**NOTE:**

For participants with Grade 3 or 4 immune-related endocrinopathy where withhold of pembrolizumab is required, pembrolizumab may be resumed when AE resolves to  $\leq$  Grade 2 and is controlled with hormonal replacement therapy or achieved metabolic control (in case of T1DM).

**Capecitabine Dose Modifications:**

**Table 2: Hematologic Toxicities**

ANC(/mm  )		Platelets (/mm  )	Modification
<1000/mm 	AND/OR	<100,000/mm 	Hold until ANC ≥ 1000/mm  and PLt ≥ 100,000  resume at 20% dose reduction
≥1000/mm 	AND	≥100,000/mm 	No dose modification

**Table 3: Mucositis, Diarrhea or Esophagitis**

Grade	Toxicities/Symptoms	Modification
1	Mucositis, esophagitis, or diarrhea	No dose modification
2	Diarrhea	No dose modification
2	Mucositis, or esophagitis	Hold until ≤ grade 1 and resume at 20% dose reduction
3	Diarrhea	Hold until ≤ grade 1; resume at 20% dose reduction
3/4	Mucositis or esophagitis	Hold until ≤ grade 1; resume at 20% dose reduction

**Table 4: Palmar-Plantar Erythrodysesthesia Syndrome (Hand and Foot Rash)**

Grade	Modification
1	No dose modification
2	Hold until symptoms resolve to grade 0 or 1 Resume a 20% dose reduction ( per treating physician's discretion )
≥3	Hold until symptoms resolve to Grade 1 or lower. Resume with dose reduction of 1 level (20% dose reduction).

**Non-hematologic Toxicity**

For other non-hematologic toxicities, dose reductions of capecitabine will be at the discretion of the investigator. A 20% dose reduction must be performed with each subsequent reduction. A maximum of 2 dose reductions will be performed.

**4.4 Concomitant Medications/Treatments**

Premedication: National Comprehensive Cancer Network (NCCN) approved prophylactic antiemetics may be given as appropriate

Medications or vaccinations specifically prohibited in the exclusion criteria are not allowed during the ongoing trial. If there is a clinical indication for one of these or other medications or vaccinations specifically prohibited during the trial,

discontinuation from trial therapy or vaccination may be required. The investigator should discuss any questions regarding this with PI. The final decision on any supportive therapy or vaccination rests with the investigator and/or the subject's primary physician.

**Acceptable concomitant medications:**

All treatments that the investigator considers necessary for a subject's welfare may be administered at the discretion of the investigator in keeping with the community standards of medical care. All concomitant medication will be recorded on the case report form (CRF) including all prescription, over-the-counter (OTC), herbal supplements, and IV medications and fluids. If changes occur during the trial period, documentation of drug dosage, frequency, route, and date may also be included on the CRF. All concomitant medications received within 28 days before the first dose of trial treatment and 30 days after the last dose of trial treatment should be recorded. Concomitant medications administered 30 days after the last dose of trial treatment should be recorded for SAEs and ECIs as defined in Section 7.2 and 7.3.3.3

**Prohibited Concomitant Medications**

Subjects are prohibited from receiving the following therapies during the Screening and Treatment Phase (including retreatment for post-complete response relapse) of this trial:

- Antineoplastic systemic chemotherapy or biological therapy
- Immunotherapy not specified in this protocol
- Chemotherapy not specified in this protocol
- Investigational agents other than pembrolizumab
- Radiation therapy

*Note: Radiation therapy to symptomatic lesions or to the brain may be allowed at the investigator's discretion.*

- Live vaccines within 30 days prior to the first dose of trial treatment and while participating in the trial. Examples of live vaccines include, but are not limited to, the following: measles, mumps, rubella, varicella/zoster, yellow fever, rabies, BCG, and typhoid vaccine.
- Systemic glucocorticoids for any purpose other than to modulate symptoms from an event of clinical interest of suspected immunologic etiology.

Subjects who, in the assessment by the investigator, require the use of any of the aforementioned treatments for clinical management should be removed from the trial. Subjects may receive other medications that the investigator deems to be medically necessary.

**Concomitant Medications/treatments to be taken with precaution**

Capecitabine is a strong CYP2C9 inhibitor. Caution should be exercised when capecitabine is co-administered with CYP2C9 substrates (see Section 8.2). Capecitabine may increase the serum concentration of vitamin K antagonists (warfarin). Patients receiving concomitant capecitabine and oral warfarin-

derivative anticoagulant therapy should have their anticoagulant response (INR or prothrombin time) monitored frequently in order to adjust the anticoagulant dose accordingly.

Pembrolizumab may be associated with Stevens-Johnson Syndrome (SJS) and Toxic Epidermal Necrolysis (TEN). Risk factors for SJS and TEN include certain medications such as anticonvulsants, sulfonamides, aminopenicillins, allopurinol, and NSAIDs. These should be taken after consultation with the treating physician. Non-medication triggers include infection, contrast media, and vaccinations. Malignancy is associated with an increased mortality rate in patients with SJS and TEN

Certain medications such as anthracyclines, alkylating agents and checkpoint inhibitors as well as radiation may be risk factors for immune-mediated myocarditis. These should be taken after consultation with the treating physician.

*Note: There are no prohibited therapies during the Post-Treatment Follow-up Phase.*

#### **4.5 Duration of Therapy**

Patients may continue to receive cycles of treatment until any of the following occur:

- Disease progression
- Development of an inter-current illness that prevents further administration of treatment
- Unacceptable adverse event(s)
- Patient decides to withdraw from either study treatment or the whole study
- The treating investigator determines that the patient should be taken off treatment for any reason (i.e. changes in condition, inability to comply with study treatment or procedures)

#### **4.6 Duration of Follow Up**

- End of treatment visit is required approximately 30 days after the last dose of pembrolizumab for the purposes of adverse event assessment.
- Patients removed from treatment for unacceptable adverse events will be followed until resolution or stabilization of the adverse event.
- Patients will be assessed every 3 months up to 2 year after discontinuation of the study drugs for PFS with visits and/or phone calls.

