#### 4.2.2 Capecitabine

Capecitabine is to be self-administered by patient, 1000 mg/m^2 PO BID Days 1-14 every 21 days. It is to be taken preferably 12 hours apart (with minimum 8 hours between doses).It is to be ingested with food or within 30 minutes of eating with 8 oz glass of water (not fruit juices). Tablets are to be swallow whole and not crushed or cut. No supportive medications are required as part of this study.

If dose is missed and next dose would normally be in less than 8 hours, then dose should be skipped entirely and marked accordingly on the medication diary (available as stand-alone document).

Patients will also record doses taken, missed, or skipped, as well as any

occurrence of vomiting, diarrhea, increased stool frequency, or rashes on the Medication Diary. This Diary will be reviewed by a member of the study team at every study visit, and any issues with compliance will be addressed. Along with the diary, patients should bring the medication bottle and any remaining tablets with them on each study visit. The Coordinator and PI will monitor for compliance. If a patient misses more than 7 consecutive doses of capecitabine due to poor adherence, the patient will be removed from study treatment. If capecitabine doses are missed, and it is < 7 doses, they may be made up within the same cycle. Patients will be given 14 days of supply at the start of study treatment. Additional capecitabine tablets will be dispensed every 3 weeks. The consent form will also ask that patients agree to keep the capecitabine pills out of reach from children and other individuals in their home.

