### **4.3 Dose Modifications**

#### **4.3.1 Dose Modification**

Adverse events (both non-serious and serious) associated with pembrolizumab exposure may represent an immunologic etiology. These adverse events may occur shortly after the first dose or several months after the last dose of treatment. Pembrolizumab must be withheld for drug-related toxicities and severe or life-threatening AEs as per Table 1 below. Dose reductions for pembrolizumab are not permitted.

Capecitabine should be withheld/dose reduced for drug-related toxicities and AEs as per Table 2, 3, 4.

See Section 4.9 for supportive care guidelines for pembrolizumab, including use of corticosteroids.

Any patient who receives at least one dose of study therapy will be evaluable for toxicity endpoints. Each patient will be assessed for the

development of toxicity according to the timeframe referenced in the Schedule of Events table). Toxicity will be assessed according to NCI's CTCAE, version 4.03.

Dosing interruptions are permitted in the case of medical / surgical events or logistical reasons not related to study therapy (e.g., elective surgery, unrelated medical events, patient vacation, and/or holidays). Subjects should be placed back on study therapy within 3 weeks of the scheduled interruption of capecitabine and 12 weeks of interruption of pembrolizumab, unless otherwise discussed with the Principal Investigator and QAM. The reason for interruption should be documented in the patient's study record.

If pembrolizumab is held for toxicity, participants are permitted to continue on protocol therapy with capecitabine alone. If capecitabine is held for toxicity, participants are permitted to continue on therapy with pembrolizumab alone.

If capecitabine doses are missed, and it is < 7 doses, they may be made up within the same cycle.

If one drug is permanently withdrawn for toxicity (i.e. the patient cannot dose reduce any further on capecitabine), then the patient should come off study completely.

Capecitabine Dose Reduction Table

Dose Level	Dose
1	1000 mg/m 
-1	800 mg/m 
-2	640 mg/m 
Stop	N/A

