 A baseline tissue biopsy of a metastatic site will be obtained for PD-L1 immunohistochemical (IHC) assessment, from all patients. An archived specimen may be used (metastatic tissue only) if collected no more than 2 months prior to registration. Otherwise fresh biopsy of metastatic lesion is mandatory at baseline and should be performed no more than 2 months prior to registration. The requirement for biopsy (fresh) may be omitted per treating physician's discretion, if the biopsy would cause undue morbidity to the patient and if enough tissue from a prior metastatic lesion (archival biopsy) is not available.

PD-L1 IHC assay from QualTek will be used for the study.  
Please refer to section 9.1 and laboratory manual for more details

 Hematology will include white blood cells (WBC) with differential, platelet count, hematocrit, and hemoglobin. To be performed within 14 days before Day1

 Serum Chemistry will include calcium, chloride, creatinine, sodium, potassium, blood urea nitrogen, bicarbonate, glucose, total bilirubin, aspartate aminotransferase (AST), alanine aminotransferase (ALT), alkaline phosphatase (ALP), albumin, and total protein. To be performed within 14 days prior to registration. Patients with liver metastasis will have additional liver function testing done on C1D7 and C1D14, which can be done locally and sent to NU for review.

 This is to be done if the patient is required to have a biopsy (in order to test for bleeding parameters before biopsy). It is to be performed and resulted before the biopsy. (Also refer to footnote 14)

 Serum or urine test for females of child-bearing potential.

 Pembrolizumab will be administered IV at the assigned dose, at Day 1 of every cycle (1cycle =21 days)

 Capecitabine will be self-administered orally by patients at a fixed dose daily on Days 1-14 twice daily, of each cycle.

 A cycle is defined as 21 days (+/- 3 days).

 Patients will be assessed every 3 months up to 2 year after discontinuation of the study drugs for PFS with visits and/or phone calls.

 concomitant medications to be recorded during screening, at the beginning of each cycle and for 30 days after end of treatment

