Thyroid function will be evaluated at baseline (performed within 14 days of Day1) and prior to the start of the next treatment cycle e.g. 4, 7, 10 etc. The tests included are TSH, freeT3, and freeT4.

Toxicity assessment to be done at the beginning of each cycle, at the end of treatment visit and for 30 days after end of treatment.

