## **7.2 Definitions & Descriptions**

### **7.2.1 Adverse Event**

An adverse event (AE) is any untoward medical occurrence in a patient receiving study treatment and which does not necessarily have a causal relationship with this treatment. An AE can therefore be any unfavorable and unintended sign (including an abnormal laboratory finding), symptom, or disease temporally associated with the use of an experimental intervention, whether or not related to the intervention.

Any worsening (i.e., any clinically significant adverse change in frequency and/or intensity) of a preexisting condition that is temporally associated with the use of the Merck's product, is also an adverse event.

Changes resulting from normal growth and development that do not vary significantly in frequency or severity from expected levels are not to be considered adverse events. Examples of this may include, but are not limited to, teething, typical crying in infants and children and onset of menses or menopause occurring at a physiologically appropriate time.

Merck product includes any pharmaceutical product, biological product, device, diagnostic agent or protocol-specified procedure, whether investigational (including placebo or active comparator medication) or marketed, manufactured by, licensed by, provided by or distributed by Merck for human use.

Adverse events may occur during the course of the use of Merck product in clinical trials, or as prescribed in clinical practice, from overdose (whether accidental or intentional), from abuse and from withdrawal.

Progression of the cancer under study is not considered an adverse event.

All adverse events that occur after the consent form is signed but before treatment allocation/randomization must be reported by the investigator if they cause the subject to be excluded from the trial, or are the result of a protocol-

specified intervention, including but not limited to washout or discontinuation of usual therapy, diet, placebo treatment or a procedure.

From the time of treatment allocation/randomization through 30 days following cessation of treatment, all adverse events must be reported by the investigator. Such events will be recorded at each examination on the Adverse Event case report forms/worksheets. The reporting timeframe for adverse events meeting any serious criteria is described in section 7.3. The investigator will make every attempt to follow all subjects with non-serious adverse events for outcome.

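### The End of Treatment safety visit is timed from the last pembrolizumab dose alone, so it comes 17 days after the last capecitabine dose in a usual last cycle and can fall due before it when a hold is never followed by resumption

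*Combined protocol and SAP*

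**What the plan says.** Section 4.6 gives the only timing for the End of Treatment visit: "End of treatment visit is required approximately 30 days after the last dose of pembrolizumab for the purposes of adverse event assessment". The End of Treatment column in the section 5.0 schedule lists examination, ECOG status, toxicity assessment, blood count and chemistry, but has no timing footnote.

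The two drugs stop on different days. Under section 5.0, footnote 8, pembrolizumab is given "at Day 1 of every cycle (1cycle =21 days"). Under section 4.2.2, capecitabine is taken "PO BID Days 1-14 every 21 days". Section 4.3.1 also separates them during a hold: "If pembrolizumab is held for toxicity, participants are permitted to continue on protocol therapy with capecitabine alone".

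The other safety rules count from the end of treatment as a whole:

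- Section 7.2.1, adverse events: "through 30 days following cessation of treatment, all adverse events must be reported by the investigator".
- Section 5.0, footnote 14, toxicity assessment: at the start of each cycle, "at the end of treatment visit and for 30 days after end of treatment".
- Section 7.2.3, serious adverse events: 90 days from the last study medication, shortened by new anticancer therapy but to no less than 30 days.
- Section 7.3.2, expedited reporting: 30 days from the last protocol treatment, and later if the event is attributed to the agents.

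**The concern.** The visit exists to assess adverse events, and it carries the last examination, blood count and chemistry in the schedule. Follow-up after it is every 3 months by visit or telephone, and the Follow-up column has no examination or laboratory tests. If the visit is dated from one drug while the other is still being taken, those tests describe a patient who is not yet 30 days off treatment, or who has not yet stopped.

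Safety and tolerability of the combination is a secondary objective (section 2.2). Capecitabine is self-administered, and section 8.2.10 lists low white cell or platelet counts, anemia and raised bilirubin among its most common effects. These are findings that a laboratory visit picks up and a telephone call may not. A hold that never leads to resumption moves the visit furthest out of place, and it does so in patients who have already had toxicity.

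**Working it through.** The plan states no figure to reproduce; the check is calendar arithmetic on its own schedule. Call the day of the last pembrolizumab dose Day 1.

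**Inputs**

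- Visit due 30 days after the last pembrolizumab dose (4.6): 1 + 30 = Day 31.
- Cycle length 21 days (5.0, footnote 10: "A cycle is defined as 21 days (+/- 3 days")).
- Capecitabine Days 1-14 of each cycle (4.2.2).
- Limit for resolution of an immune-related event during a hold: 12 weeks from the last dose (Table 1, general instruction 2), so 1 + 84 = Day 85.
- Adverse event window: 30 days after treatment ends (7.2.1).

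**Formulas**, with k the number of capecitabine-alone cycles given after the last pembrolizumab dose:

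- Last capecitabine day = 14 + 21k
- Gap from last capecitabine to visit = 31 − (14 + 21k) = 17 − 21k
- Day the 30-day window closes = 14 + 21k + 30 = 44 + 21k

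| k | Last capecitabine | Visit as written | Gap (days) | Window closes |
|---|---|---|---|---|
| 0 | Day 14 | Day 31 | 17 after | Day 44 |
| 1 | Day 35 | Day 31 | 4 before | Day 65 |
| 2 | Day 56 | Day 31 | 25 before | Day 86 |
| 3 | Day 77 | Day 31 | 46 before | Day 107 |

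**Usual last cycle (k = 0).** The visit falls 44 − 31 = 13 days before the window closes.

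**Sensitivity**

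- Section 4.3.1 also says: "If capecitabine doses are missed, and it is < 7 doses, they may be made up within the same cycle". Six made-up doses at two a day add 3 days, so the last dose is about Day 17. The gap is then 31 − 17 = 14 days, which is 16 short of 30.
- A patient who stops capecitabine early in the last cycle has a longer gap, up to about 30 days.
- If the first capecitabine-alone cycle starts 3 days early (Day 19), its last dose is on Day 19 + 13 = 32, and the visit is still due 1 day before it.
- A cycle starting exactly on Day 85 would end on Day 98, 67 days after the visit was due.

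**Whether k ≥ 1 can be a patient's final state.** Section 4.3.1 takes a patient off study when one drug is permanently withdrawn for toxicity, so the case needs a temporary hold that never leads to resumption. The protocol provides two routes: progression during the hold (4.5), and an event unresolved at 12 weeks, when Table 1 discontinues pembrolizumab and 4.3.1 then ends study participation. One held cycle is enough to put the due date before the last study drug.

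**The case against.** The strongest reply is that adverse event collection does not depend on this visit. Section 7.2.1 requires reporting for 30 days after treatment ends. Footnote 14 names the visit and the 30-day period as separate requirements. Serious events run longer, and sections 7.1 and 4.6 follow events onward to resolution or stabilization. The Follow-up column also marks toxicity assessment. Nothing says that the visit must close the 30-day window. This stands: a reader might infer that toxicity is under-counted, but the documents show only that scheduled examination and laboratory tests stop before the window does.

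Second, a patient still on capecitabine is on treatment, so a site would probably not call an End of Treatment visit on Day 31, and during a hold nobody knows which pembrolizumab dose will prove to be the last. Such a patient keeps the per-cycle examination, blood count, chemistry and toxicity assessment. This also stands as to monitoring. It does not rescue the wording: once treatment ends without resumption, section 4.6 gives a date already past, and a site that sensibly delays the visit departs from the text. A reader might go further and infer that these patients have no post-treatment safety visit. They do. The End of Treatment column still requires it; only its timing fails.

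Third, counting from pembrolizumab could be deliberate, given the 26-day half-life in section 1.2.1 and the late immune-related events noted in 4.3.1. Neither is a reason to examine the patient sooner after capecitabine, and counting from the later drug never brings the visit closer to the last pembrolizumab dose.

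Finally, the word approximately in section 4.6 gives latitude, but hardly 13 days, and not a visit due before the last dose.

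**Conclusion.** The point holds as an inconsistency in timing that is cheap to correct. In a usual last cycle the visit comes 17 days after the last study drug and 13 days before the 30-day window closes. This assumes that capecitabine is taken through Day 14 and that the visit is held on the nominal day, and it applies to most patients who complete their last capecitabine course. After an unresumed hold the due date precedes the last study drug by 4 days (one capecitabine-alone cycle) to 46 days (three cycles). The 46-day figure is close to the 12-week limit and is not a typical case.

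How many patients fall in the second group cannot be derived, because the documents give no hold rate. A reader might count everyone with a hold, but that is too many: patients who resume pembrolizumab are unaffected, and events that require immediate permanent discontinuation take the patient off study with no capecitabine-alone period. No loss of adverse event data is demonstrated. What remains is a risk that laboratory and examination findings after capecitabine are not captured at a scheduled visit.

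**What to change.** In section 4.6, count the visit from the last dose of either study drug, whichever is later, and add the same timing to the End of Treatment column of section 5.0. Footnotes 12 and 14 already count from end of treatment; they need only the same definition of that date. The visit then falls on Day 44 in a usual last cycle, and on Days 65, 86 and 107 after one, two and three capecitabine-alone cycles, so it always follows the end of treatment and coincides with the close of the 30-day window in 7.2.1.

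The cost is wording, with no added visit or test. The visit moves 44 − 31 = 13 days later in usual patients. Section 4.4 prohibits no therapy during post-treatment follow-up, so a few more patients may have started another treatment by then, which can blur attribution. The End of Treatment column also marks tumor measurements, so the amendment should state whether imaging moves with the visit.
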